4.2 Exclusion Criteria

1. Participants in cohort A may not have had prior therapy for their disease. Participants in cohort B may not have had more than 1 cycle of systemic therapy (cisplatin or carboplatin + etoposide). Participants in cohort C and D should not have had more than one prior regimen of chemotherapy.
2. For participants entering cohorts C or D, prior treatment-related toxicities should have resolved to grade 1 or baseline (with the exception of anemia (as per inclusion criteria, alopecia, and neuropathy (≤ grade 2 allowed)).
3. Participants who have had a CR after pre-study therapy are not eligible for study.
4. No thoracic radiation > 3000 cGy allowed.
5. Prior radiation or surgery must have completed at least 2 weeks prior to initiation of therapy and all toxicities or complications from these must have resolved to baseline or grade 1 prior

to starting therapy (with the exception of anemia (as per inclusion criteria, alopecia, and neuropathy (\leq grade 2 allowed)).

6. No stroke, myocardial infarction, or major surgery within 3 months of starting on therapy.
7. Participants who are receiving any other investigational agents or have received investigational therapy or any anti-cancer monoclonal antibody (mAB) within 4 weeks prior to the 1st dose of pembrolizumab.
8. Has received prior therapy with an anti-PD-1, anti-PD-L1, or anti-PD-L2 agent.
9. Has active autoimmune disease that has required systemic treatment in the past 2 years (i.e. with use of disease modifying agents, corticosteroids or immunosuppressive drugs). Replacement therapy (eg., thyroxine, insulin, or physiologic corticosteroid replacement therapy for adrenal or pituitary insufficiency, etc.) is not considered a form of systemic treatment.
10. Has known history of non-infectious pneumonitis which required steroids, or any evidence of current, non-infectious pneumonitis.
11. Has an active infection requiring systemic therapy.
12. Has a diagnosis of immunodeficiency or is receiving systemic steroid therapy or any other form of immunosuppressive therapy within 7 days prior to the first dose of trial treatment.
13. Has a known history of active TB (Bacillus Tuberculosis)
14. History of allergic reactions attributed to compounds of similar chemical or biologic composition to pembrolizumab, cisplatin, carboplatin, or etoposide.
15. Uncontrolled intercurrent illness including, but not limited to, ongoing or active infection, symptomatic congestive heart failure, unstable angina pectoris, cardiac arrhythmia, or psychiatric illness/social situations that would limit compliance with study requirements.
16. Has known psychiatric or substance abuse disorders that would interfere with cooperation with the requirements of the trial.
17. Is pregnant or breastfeeding, or expecting to conceive or father children within the projected duration of the trial, starting with the pre-screening or screening visit through 120 days after the last dose of trial treatment.
18. Has known active Hepatitis B (e.g., HBsAg reactive) or Hepatitis C (e.g., HCV RNA [qualitative] is detected).
19. Has a known history of Human Immunodeficiency Virus (HIV) (HIV 1/2 antibodies).
20. Has received a live vaccine within 30 days of planned start of study therapy *Note: Seasonal influenza vaccines for injection are generally inactivated flu vaccines and are allowed; however intranasal influenza vaccines (e.g., Flu-Mist®) are live attenuated vaccines, and are not allowed.*
21. Has a known additional malignancy that is progressing or requires active treatment or has required active treatment within the last 2 years. Exceptions include basal cell carcinoma of

the skin or squamous cell carcinoma of the skin that has undergone potentially curative therapy or in situ cervical cancer or in situ bladder cancer.

22. Has a paraneoplastic syndrome other than SIADH (hyponatremia).
23. Evidence of interstitial lung disease

4.3 Inclusion of Women and Minorities

Both men and women of all races and ethnic groups are eligible for this trial.

4.4 Subject Recruitment

Target Enrollment for this study is 60 patients. Each cohort will consist of 15 patients. The inclusion and exclusion criteria in this study should not have a negative effect on the enrollment of these populations.

Patients will be recruited from physicians at the NYULMC Perlmutter Cancer Center (PCC). Consenting, screening, and treatment take place at the NYULMC PCC under the supervision of the Overall PI. Prospective subjects receive detailed information about this study its investigational nature, required study procedures, alternative treatments, risks and potential benefits of the study. They also receive the informed consent document to read. All questions are answered by the Principal Investigator.

The Principal Investigator will:

1. Obtain signed and dated informed consent from the potential subject before any study specific procedures are performed.
2. Determine patient eligibility See Section 4.1 and Section 4.2
3. Submit registration to NYULMC Perlmutter Cancer Center CTO
4. Receive registration confirmation from the Research Coordinator at NYU Perlmutter Cancer Center CTO, including a unique study identification number assigned to the patient by the research coordinator, which will be distributed to the study team upon registration.

Recruitment and consenting will take place in a private area such as an exam room to protect the patient's privacy. The informed consent process and documentation follows the established procedures of the NYULMC PCC CTO.

4.4.1 Informed Consent

Consent will be obtained only by a participating investigator who has completed requisite training for human subject research and has been instructed by the Principal Investigator about the patients and address any questions or concerns prior to obtaining written informed consent for participation and HIPAA authorization.

Patients will be given adequate time to read the consent form. They will be given time to ask questions about the study in private exam rooms. Questions will be answered by a participating physician, or qualified research study team member all of whom have completed requisite training for human subject research. Investigators will review the informed consent form with patients and address any questions

or concerns prior to obtaining written informed consent for participation. Investigators will stress that participation in the study is completely voluntary and will not affect the care patients receive or result in any loss of benefits to which patients are otherwise entitled.

For non-English speaking patients, institutional translation services will be utilized. For these patients the consent letter and all other information will be administered orally and a witness, not related to the research project, will be present while the oral presentation is given. A short form will be utilized for the subject to sign in his/her name and the translator and/or witness must sign the short form. The translator will also sign the main consent form.

For patients who cannot read. A witness, not related to the research study will be present. The consent will be read to the patient. The patient will also be allowed to ask any questions s/he may have. The investigator will ask the patient questions to ensure s/he understands the study. If the investigator determines the subject understands the study, the patient will mark an X where his/her name would go and the witness will sign the consent form

4.4.2 Documentation of Consent

The Principal Investigator or IRB approved sub-investigator will be responsible for documentation in the medical record that consent has been obtained from all participants. A signed copy of the consent form will be given to each participant. Original consent forms will be stored in the subject's medical chart.

4.4.3. Multi-Site Surveillance

As the lead investigator in a multi-site trial, the Overall Principal Investigator is responsible for organizing and conducting monthly teleconferences with all participating sites. The PI will also be responsible for including data from all of the participating sites within the overall trial's six month Data and Safety Monitoring report to the DSMC to include minutes from monthly PI teleconferences. Each participating site will be responsible for submitting the results and recommendations from the DSMC's six month review to their IRB of record at the time of continuing review.

4.4.4. Patient Informed Consent at Additional Sites

The Principal Investigator at each participating site will identify the physician members of the study team who will be obtaining consent and signing the consent form for this research study. It is NYULMC policy that Nurses and Fellows cannot obtain consent to greater than minimal risk trials, unless Fellows are listed as co-investigators.

The Investigator must ensure that each participant, is fully informed about the nature and objectives of the study and possible risks associated with participation. All participants must be provided a consent form describing this study and providing sufficient information for participants to make an informed decision about their participation in this study. The formal consent of a participant, using the IRB approved consent form, must be obtained before the participant is involved in any study-related procedure. The consent form must be signed and dated by the participant or the participant's legally authorized representative (if applicable), and by the person obtaining the consent. The participant must be given a copy of the signed and dated consent document. The original signed copy of the consent document must be retained in the medical record or research file.

All parties will ensure protection of participant personal data and will not include participant names on any sponsor forms, reports, publications, or in any other disclosures, except where required by laws. In case of data transfer, NYULMC PCC will maintain high standards of confidentiality and protection of participant personal data.

The informed consent form must be in compliance with ICH/GCP, local regulatory requirements, and legal requirements.

The informed consent form used in this study, and any changes made during the course of the study, must be prospectively approved by both the NYU IRB and Merck before use.

4.5 Registration Procedures

4.5.1. General Guidelines

Each patient must sign and date an informed consent form before undergoing any study specific procedure unless a procedure is being performed as part of the patient's standard of care.

Enrollment in the study requires that all inclusion and exclusion criteria have been met. Enrollment occurs upon confirmation of registration from the NYULMC PCC Clinical Trials Office. The following materials must be submitted to the Research Coordinator for registration:

1. Complete signed and dated informed consent form
2. Complete signed and dated informed consent checklist
3. Complete signed and dated eligibility checklist
4. All supporting documentation verifying each criterion has been met

Registration will occur within 24 hours of research coordinator receipt of all of the above documents. A written confirmation of enrollment including a unique study identification number assigned by the research coordinator will be distinguished to the study team upon registration.

Pretreatment evaluation will therefore be as directed by standard clinical practice. Eligible subjects will be entered on study by the study coordinator.

All patients will be required to sign a written informed consent prior to being registered on this study. Every effort will be made to answer questions raised by patients and their families or advocates regarding the protocol and alternative therapies prior to asking a patient to sign the consent form.

Once eligibility is verified, a unique patient study number will be issued within 24 hours of receiving all required registration material. The patient will not be identified by name. This is the point, at which, the patient is considered on study. Subjects must not start any protocol procedures prior to registration.

Issues that would cause treatment delays should be discussed with the Overall Principal Investigator.

4.5.2 Patient Registration at Other Participating Institutions

The Principal Investigator (PI) at each participating site will identify the physician members of the study team who will be obtaining consent and signing the consent form for therapeutic protocols. It is NYULMC policy that Nurses and Fellows cannot obtain consent to greater than minimal risk trials.

Enrollment at additional sites can occur once each site's IRB has approved this protocol, a copy of each site's IRB approval, Citi training certificates, Medical Licenses and signed CVs are provided to NYULMC Perlmutter Cancer Center Clinical Trials Office. Once, all required documents are provided to NYULMC PCC Clinical Trials Office an activation notification will be sent to the PI and research coordinator at that site.

Central registration for this study will take place at NYULMC PCC.

Each patient must sign and date an informed consent form before undergoing any study specific procedure unless a procedure is being performed as part of the patient's standard of care. Once a patient has signed consent, each site must notify the NYULMC PCC Research Coordinator and forward a copy of the signed consent to NYULMC PCC Clinical Trials Office within 24 hours.

1. Complete signed and dated informed consent form
2. Complete signed and dated informed consent checklist
3. Complete signed and dated eligibility checklist
4. All supporting documentation verifying each criterion has been met

Registration will occur within 24 hours of research coordinators receipt of all of the above documents. Once eligibility is verified, a unique subject study number will be issued within 24 hours of receiving all required registration material. This number is unique to the participant and must be written on all data and correspondence for the participant. The NYULMC PCC Clinical Trials Office will return a signed eligibility confirmation worksheet with the subject's unique study number. The subject will not be identified by name. This is the point, at which, the patient is considered on the study.

Registrations must occur prior to the initiation of protocol therapy. Any participant not registered to the protocol before protocol therapy begins will be considered ineligible and registration will be denied.

An investigator will confirm eligibility criteria and a member of the study team will complete the protocol-specific eligibility checklist.

Following registration, participants may begin protocol therapy. Issues that would cause treatment delays should be discussed with the Overall Principal Investigator, [name]. If a participant does not receive protocol therapy following registration, the participant's registration on the study must be canceled.

4.6 Early Withdrawal of Subjects

4.6.1 When and How to Withdraw Subjects

Early trial termination will be the result of the criteria specified below:

1. Quality or quantity of data recording is inaccurate or incomplete
2. Poor adherence to protocol and regulatory requirements
3. Incidence or severity of adverse drug reaction in this or other studies indicates a potential health hazard to subjects
4. Plans to modify or discontinue the development of the study drug

In the event of Merck's decision to no longer supply study drug, ample notification will be provided so that appropriate adjustments to subject treatment can be made.

Every effort should be made to obtain information on subjects who withdraw from the study. The date the participant was removed, must be documented.

4.6.2 Withdrawal/Discontinuation

When a subject discontinues/withdraws prior to trial completion, all applicable activities scheduled for the final trial visit should be performed at the time of discontinuation. Any adverse events which are present at the time of discontinuation/withdrawal should be followed in accordance with the safety requirements outlined in Section 10 –Adverse Event reporting. Subjects who a) attain a CR or b) complete 24 months of treatment with pembrolizumab may discontinue treatment with the option of

restarting treatment if they meet the criteria specified in Section 6.6.10.6. After discontinuing treatment following assessment of CR, these subjects should return to the site for a Safety Follow-up Visit (described in Section 6.6.10.3 and then proceed to the Follow-Up Period of the study (described in Section 6.6.10.4.

5 Study Drug

5.1 Description

Pembrolizumab (Keytruda, MK-3475, previously known as SCH 900475) is a potent and highly selective humanized mAb of the IgG4/kappa isotype designed to directly block the interaction between PD-1 and its ligands, PD-L1 and PD-L2.

5.2 Trial Treatment

The treatment to be used in this trial is outlined below:

Table 2 Trial Treatment

Cohort	Drug	Dose/Potency	Dose Frequency	Route of Administration	Regimen/Treatment Period	Use
A and B ¹	Pembrolizumab	200 mg	Q3W	IV infusion	Day 1 of each 3 week cycle	Experimental
	carboplatin OR	AUC 6	Q3W	IV infusion	Day 1 of each 3 week cycle	Standard care
	cisplatin	75 mg/m ²	Q3W	IV infusion	Day 1 of each 3 week cycle	Standard of care
	Etoposide	100 mg/m ²	Q3W	IV infusion	Days 1, 2, 3 of each 3 week cycle	Standard of care
C	Pembrolizumab	200 mg	Q3W	IV infusion	Day 1 of each 3 week cycle	Experimental
D	Pembrolizumab	200 mg	Q3W	IV infusion	Day 1 of each 3 week cycle	Experimental

¹for cohort A, the number of total cycles of chemotherapy will be 4-6 total, while pembrolizumab will continue as long as disease has not progressed or patient not removed from study for other reasons for up to 2 years. For cohort B, patients should have received 1 cycle platinum + etoposide prior to entry onto study, so the total number of cycles during study will be 3-5 (such that the TOTAL number of cycles on or off study is a MINIMUM of 4 and a MAXIMUM of 6).

Trial treatment should begin on the day of randomization or as close as possible to the date on which treatment is allocated/assigned.

5.3 Treatment Regimen

Pembrolizumab will be administered every 3 weeks, with 21 consecutive days defined as a treatment cycle. For cohort A, pembrolizumab will be administered together with ALL cycles of chemotherapy (4-6 total cycles). For cohort B, pembrolizumab will be administered together with cycles during study which may be 3-5 additional cycles. Specifically, participants in cohort B should have received 1 prior cycle of chemotherapy. These patients should be continued on the same treatment regimen while on

study to a TOTAL of 3-5 cycles of chemotherapy (on and off study). For cohorts C and D, pembrolizumab will be administered as monotherapy (see below).

Cisplatin (75 mg/m²) or carboplatin (AUC 6) will be administered every 3 weeks, with 21 consecutive days defined as a treatment cycle. Either cisplatin or carboplatin will be administered together with etoposide 100 mg/m² given on days 1, 2, and 3 as per institutional standards of care. Criteria for treatment and dose modifications for each of these drugs will occur as per institutional standards of care.

Platinum and etoposide treatments will be given only in cohorts A and B. Cohorts C and D will have pembrolizumab monotherapy following completion of standard therapy.

Cohort A: pembrolizumab + carboplatin or cisplatin + etoposide X 4-6 cycles followed by pembrolizumab monotherapy for up to 2 year (34 cycles post-combination therapy).

Cohort B: Participants may have received 1 cycle of prior therapy. They will be continued on the SAME treatment regimen (carboplatin or cisplatin + etoposide) together with pembrolizumab for up to a TOTAL of 4-6 cycles (including cycles prior to study). Treatment with the combination should start no sooner than 3 weeks and no later than 5 weeks from the start of the last cycle of chemotherapy. Maintenance pembrolizumab will continue following completion of combination therapy for up to 2 years (34 cycles post-combination therapy).

FOR COHORTS A AND B ONLY: Initial enrollment will include only 3 participants, who may be enrolled into either cohort A or B. Once these three participants have cleared cycle 1, an additional 3 participants may be enrolled into either cohort A or B if no DLTs are seen. If < 2 DLTs are seen in the first 6 participants, enrollment to the rest of the cohorts will proceed. If ≥ 2 DLTs are seen, enrollment will be halted and discussion of dosing change with Merck and the overall PI will occur prior to further enrollment. Based on safety data to date with other platinum-based regimens, we do not anticipate interactions that would necessitate dosing change, so there will not be pre-specified dose reductions planned. Cohorts A and B will be pooled for the purposes of DLT evaluation as the treatment regimen after study initiation is identical.

Cohort C: participants will have previously received 4-6 cycles of platinum-based therapy and have stable disease. In addition, these patients must not be candidates for further consolidation thoracic radiotherapy or PCI. Pembrolizumab treatment should start no sooner than 2 weeks and no later than 6 weeks from the start of the last cycle of chemotherapy. Therapy will continue for up to 34 cycles (2 years).

Cohort D: participants will have previously received 4-6 cycles of platinum-based chemotherapy and thoracic radiation therapy or PCI or both. Pembrolizumab treatment should start no sooner than 2 weeks and no later than 6 weeks from the start of the last dose of radiation. Therapy will continue for up to 34 cycles (2 years).

Treatment will be administered on an outpatient basis. Reported adverse events and potential risks are described in Section 1.8.1. Appropriate dose modifications are described in Section 5. No investigational or commercial agents or therapies other than those described below may be administered with the intent to treat the participant's malignancy.

All patients will be required to have a tissue biopsy within 3 weeks of study entry and after completion of prior therapy (see section 6.6.7.1). For cohort A, this time frame could be up to 6 weeks.

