5. TREATMENT REGIMEN

- All participants will be treated with cisplatin (75 mg/m²) or carboplatin (AUC 6) + etoposide 100 mg/m² IV every 3 weeks for up to 6 cycles (minimum of 4 cycles, maximum of 6).
- Pembrolizumab will be dosed at 200 mg IV fixed dose every 3 weeks until progression or for up to 2 years of therapy.
- Thoracic radiotherapy will be given per institutional standards (dose and duration may vary for individual participants).

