5.5 Agent Administration

5.5.1 Pembrolizumab

Pembrolizumab 200 mg will be administered as a 30 minute IV infusion on day 1 of every 21 day cycle.

After completion of chemotherapy, pembrolizumab will be administered as monotherapy for up to a total of 34 cycles (2 years of monotherapy).

Sites should make every effort to target infusion timing to be as close to 30 minutes as possible. However, given the variability of infusion pumps from site to site, a window of -5 minutes and +10 minutes is permitted (i.e., infusion time is 30 minutes: -5 min/+10 min).

The Pharmacy Manual for pembrolizumab contains specific instructions for the preparation of the pembrolizumab infusion fluid and administration of infusion solution.

5.5.2 Cisplatin or carboplatin and etoposide.

Cisplatin, carboplatin, and etoposide should be administered as per institutional standards.

Cisplatin 75 mg/m² will be administered as an IV infusion per institutional standards on day 1 of every 21 day cycle for up to 6 cycles for cohort A and for up to 5 cycles for cohort B (total number of cycles of chemotherapy on and off study should not total more than 6)

Carboplatin AUC 6 will be administered as an IV infusion per institutional standards on day 1 of every 21 day cycle for up to 6 cycles for cohort A and for up to 5 cycles for cohort B (total number of cycles of chemotherapy on and off study should not total more than 6)

Etoposide 100 mg/m² will be administered as an IV infusion per institutional standards on day 1, day 2, and day 3 of every 21 day cycle for up to 6 cycles for cohort A and for up to 5 cycles for cohort B (total number of cycles of chemotherapy on and off study should not total more than 6).

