5.9 Criteria for Taking a Participant Off Protocol Therapy

Duration of therapy will depend on individual response, evidence of disease progression and tolerance. In the absence of treatment delays due to adverse event(s), treatment with platinum + etoposide may continue for UP TO 6 TOTAL CYCLES (on and off therapy) but may be stopped at 4 cycles at investigator discretion based on tolerability. Treatment may be stopped at any time if one of the below criteria applies. Pembrolizumab may continue for up to 34 cycles (2 years) or until one of the following criteria applies:

- Disease progression
- Intercurrent illness that prevents further administration of treatment
- Unacceptable adverse event(s)
- Participant demonstrates an inability or unwillingness to comply with the oral medication regimen and/or documentation requirements
- Participant decides to withdraw from the protocol therapy
- General or specific changes in the participant's condition render the participant unacceptable for further treatment in the judgment of the treating investigator

Participants will be removed from the protocol therapy when any of these criteria apply UNLESS THERE IS ISOLATED CNS PROGRESSION (Section 5.11.2). The reason for removal from protocol therapy, and the date the participant was removed, must be documented in the case report form (CRF). Alternative care options will be discussed with the participant.

In the event of unusual or life-threatening complications, treating investigators must immediately notify the Overall PI, [name], [contact] .

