6.6.9.2 Treatment Period

The treatment period consists of up to 34 cycles (2 year) of treatment with pembrolizumab in addition to up to 5 (cohort B) or 6 (cohort A) cycles of chemotherapy. Cohort A and B patients may also have treatment with pembrolizumab interrupted for consolidation thoracic radiation and/or prophylactic cranial irradiation as indicated. Re-treatment after cessation of pembrolizumab following a CR will also continue for up to 1 year (See section 6.6.9.6).

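### Section 5.3 gives cohort B a chemotherapy total of 3-5 cycles on and off study; its own inputs and the rest of the protocol give 4-6

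*Combined protocol and SAP*

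**What the plan says.** The first paragraph of section 5.3 (Treatment Regimen) makes three statements about cohort B. Pembrolizumab is given "together with cycles during study which may be 3-5 additional cycles". Participants should have had 1 prior cycle of chemotherapy. They then continue the same regimen to a "TOTAL of 3-5 cycles of chemotherapy (on and off study").

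Other sections state the rule as follows:

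- Section 5.3, Cohort B paragraph: up to a "TOTAL of 4-6 cycles (including cycles prior to study").
- Section 5.2, Table 2 footnote, repeated in the Appendix B pharmacy manual: 3-5 cycles during study, such that "the TOTAL number of cycles on or off study is a MINIMUM of 4 and a MAXIMUM of 6".
- Synopsis, Treatment Regimen, for all participants: "for up to 6 cycles (minimum of 4 cycles, maximum of 6").
- Section 5.5.2: up to 5 on-study cycles in cohort B, and the "total number of cycles of chemotherapy on and off study should not total more than 6".
- Section 5.9: up to 6 in total, and treatment "may be stopped at 4 cycles at investigator discretion based on tolerability".
- Section 6.6.9.2: "up to 5 (cohort B) or 6 (cohort A) cycles of chemotherapy".

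On prior exposure, inclusion criterion 3 (section 4.1) requires cohort B to have completed 1 cycle, and exclusion criterion 1 (section 4.2) bars more than 1. Footnote b of the cohort A and B calendar (section 7) nevertheless sets 2-4 on-study cycles for cohort B participants who had 2 cycles beforehand. Section 1.6 describes cohort B as starting after two cycles, and sections 1.7 and 6.7.1.1 say 1-2.

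**The concern.** The 5.3 sentence is a dosing instruction, and it conflicts with the paragraph it sits in. Because it says explicitly that cycles both on and off study count, 3-5 cannot be read as the on-study number alone. A site following it literally could electively stop a cohort B participant after 3 cycles in total, or withhold a sixth cycle that the rest of the protocol allows.

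Some courses cannot satisfy both rules. A participant given 6 cycles meets Table 2 and breaches the 5.3 sentence. One electively stopped at 3 meets the sentence and falls below the minimum of 4. The protocol does not say which statement prevails, so either course invites a deviation query. Uneven chemotherapy exposure could also carry into cohort B's progression-free and overall survival, which are secondary endpoints.

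The calendar clause is a separate inconsistency. A coordinator working from the calendar could infer that patients with 2 prior cycles may be enrolled.

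**Working it through.** **Inputs for cohort B**

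- Prior cycles: 1 (section 5.3; section 4.1 item 3; section 4.2 item 1).
- On-study cycles: 3 to 5 (section 5.3, first paragraph; Table 2 footnote).
- Stated total on and off study: 3 to 5 (section 5.3, first paragraph).

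**Attempt to reproduce the stated total**

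Total = prior + on study.

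- Minimum: 1 + 3 = 4.
- Maximum: 1 + 5 = 6.

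The result is 4-6, so 3-5 is not reproduced. Two other readings also fail:

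- Taking 3-5 as the true total implies 3 - 1 = 2 to 5 - 1 = 4 cycles on study. That contradicts the 3-5 additional cycles in the same paragraph.
- Assuming 2 prior cycles gives 2 + 3 = 5 to 2 + 5 = 7, which is not 3-5 and exceeds the cap of 6.

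**Check against the other sections**

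| Place | What it gives for cohort B | Total implied |
|---|---|---|
| 5.3, first paragraph, inputs | 1 prior + 3-5 | 4-6 |
| 5.3, first paragraph, stated total | 3-5 | 3-5 |
| 5.3, Cohort B paragraph | 4-6 including prior cycles | 4-6 |
| Table 2 footnote and pharmacy manual | 3-5 on study | 4-6 |
| Synopsis | minimum 4, maximum 6 | 4-6 |
| 5.5.2 | up to 5 on study, total at most 6 | maximum 1 + 5 = 6 |
| 5.9 | up to 6, may stop at 4 | 4-6 |
| 6.6.9.2 | up to 5 on study | maximum 1 + 5 = 6 |
| Calendar footnote b, 1 prior | 3-5 on study | 4-6 |
| Calendar footnote b, 2 prior | 2-4 on study | 2 + 2 = 4 to 2 + 4 = 6 |

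Only the stated total in the first paragraph of 5.3 departs from 4-6.

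**Who is affected**

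- Literal rule: {3, 4, 5}. Intended rule: {4, 5, 6}. Both: {4, 5}.
- Literal rule only: 3, one cycle under the minimum.
- Intended rule only: 6, capped at 5 under the literal rule, one cycle fewer.
- Each discrepancy is one 21-day cycle.
- The 2-prior-cycle branch applies to 0 of the 15 planned cohort B participants if the eligibility criteria are followed.

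**Reach into the analysis**

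The schema places cohort B's second biopsy after cycle 1 and before pembrolizumab. The number of later cycles therefore cannot alter the paired PD-L1 change, and no sample-size or power input depends on the cycle total.

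**The case against.** The best counter-argument is that the protocol already supplies the answer. The Cohort B paragraph of the same section, the treatment table, the synopsis, the calendar and the pharmacy manual all lead to 4-6, so a site would have to overlook all of them to act on 3-5. That makes the intended value certain and limits the likely harm. It does not remove a contradictory instruction from the section that sets treatment.

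Second, 6 is a ceiling and not an entitlement: stopping at 5 complies with the intended rule. That is right for an investigator who chooses to stop. The literal sentence, however, takes away the option of a sixth cycle, which is a different matter.

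Third, section 5.9 already permits fewer than 4 cycles for progression, unacceptable toxicity or withdrawal, and section 5.3.2 generally ends chemotherapy after a delay of more than 4 weeks. This also stands. It confines the lower-end problem to elective stops at exactly 3.

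Fourth, the caps in 5.5.2 and 6.6.9.2 say nothing about the minimum, and a cap of 6 is by itself compatible with a total of 3-5. They do bear on the upper end: 5 on-study cycles after 1 prior cycle is 6, which the 5.3 sentence forbids.

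Finally, the 2-prior-cycle wording has no effect when eligibility is observed, and the calendar branch still adds up to 4-6. That is accepted. It remains a dosing rule for patients who cannot enrol.

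**Conclusion.** The concern holds. The cohort B total in the first paragraph of 5.3 is wrong as written: it should be 4-6 on and off study, with 3-5 the on-study part. This rests only on the protocol's own 1 prior cycle and 3-5 additional cycles.

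The practical effect is limited to participants who would be stopped electively at 3 or would otherwise receive a sixth cycle. How many that would be cannot be derived from the documents. Any effect on later survival outcomes is possible but unquantified. The primary PD-L1 comparison, sample size and power are untouched. The calendar's 2-prior-cycle clause conflicts with eligibility and could influence PD-L1 change only if someone were enrolled against the criteria. The correction should be made because the error sits in an operative chemotherapy instruction.

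**What to change.** In the first paragraph of section 5.3, set the cohort B total to 4-6 cycles on and off study, of which 3-5 are on study. In section 7, delete the clause for 2 prior cycles from footnote b of the cohort A and B calendar. As clerical tidying in the same amendment, change the descriptions of cohort B in sections 1.6, 1.7 and 6.7.1.1 to exactly 1 prior cycle, matching section 4.1 item 3 and section 4.2 item 1.

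The cost is amendment wording in five sentences. No new data, procedures or analyses are needed.
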